4.2 Intervention

4.2.1 Mastectomy with Immediate Tissue Expander Placement

Patients will undergo mastectomy and axillary dissection with immediate tissue expander placement. As is the current practice at MSKCC, patients receiving adjuvant chemotherapy will undergo expansion during chemotherapy, with exchange for a permanent implant to be performed approximately one month after chemotherapy and radiation to begin approximately one month after exchange. Patients who receive neoadjuvant chemotherapy will undergo —rapid expansion of the expander and begin radiation at least 4 weeks following surgery, although it may be performed sooner if the patient has recovered from surgery and the treating physician deems it safe to proceed with treatment. In these patients, exchange for the permanent implant will occur at the discretion of the treating plastic surgeon (approximately 4-8 months after the end of radiation).

4.2.2 Multi-beam IMRT

Multi-beam IMRT will be performed approximately one month (but no sooner than 2 weeks) after exchange in Group 1. Multi-beam IMRT will be performed at least 4 weeks after mastectomy in Group 2, although it may be performed sooner if the patient has recovered from surgery and the treating physician deems it safe to proceed with treatment. The target volume for IMRT will be contoured according to guidelines specified in Appendix 2. All patients will receive 50-50.4 Gy in 25-28 fractions, which is the standard dose and fractionation for breast IMRT in our department. Prior to each daily treatment, the reproducibility of the patient's position will be verified by kilovoltage (kV) x-rays or Align RT®, an FDA-approved in-room video-based localization system.

A subset of 10 left-sided patients will receive $^{13}\text{N-NH}_3$ PET scans within the radiation simulation session. A CT for coronary calcium scoring and a low-dose CT for attenuation correction will also be obtained at this time. Myocardial blood flow will be measured during rest and at peak stress with $^{13}\text{N-NH}_3$ as a perfusion tracer. A follow-up $^{13}\text{N-NH}_3$ PET study with low-dose CT for attenuation correction will be obtained 12-18 months (\pm 6 months) post-IMRT.

4.2.3 MRI

MRI studies will be strongly recommended but not required. At the time of study consent, if a patient chooses not to participate in the the portion of the study that recommends MRIs, then they will not be approached about follow-up MRIs following radiation.

Baseline MRI: MRI scans will be performed at the baseline assessment point and acquired on the Philips 3T scanner (70 cm bore size diameter), located in the Department of Radiation Oncology Main

Campus. All MRIs will be performed in the prone position with a dedicated 16-channel prone breast coil. The scanning field-of-view will include both breasts and coverage will encompass supraclavicular region excluding the descending thoracic aorta.

The following 5 sequences will be obtained for silicone implants. All MRIs will include the bilateral breasts.

- 1) Axial non-fat-saturated 3D T1-weighted fast field echo (FFE) (TR/TE = minimum/2.3 ms)
- 2) Axial non-fat-saturated 3D T2-weighted turbo spin echo (TSE) (TR/TE = 2000/minimum ms)
- 3) Axial 2D IR water saturation (silicone is hyperintense) (TR/TE = minimum/65 ms)
- 4) Axial fat-saturated 3D T1-weighted FFE image (silicone is hypointense and water is hyperintense) (TR/TE = minimum), and
- 5) Contrast-enhanced dynamic axial fat-saturated 3D T1-weighted FFE (TR/TE=minimum)

For saline implants, the 4 sequences will include:

- 1) Axial non-fat-saturated 3D T1-weighted FFE (TR/TE = minimum/2.3 ms)
- 2) Axial non-fat-saturated 3D T2-weighted TSE (TR/TE = 2000/minimum ms)
- 3) Axial fat-saturated 3D T1-weighted FFE (TR/TR = minimum), and
- 4) Contrast-enhanced dynamic axial fat-saturated 3D T1-weighted FFE

There will be a total of four dynamics at a temporal resolution of ~ 60-90 seconds. All sequences will be acquired with an isotropic voxel size of 1x1x1 mm³ except the axial 2D IR water saturation sequence, which will be acquired with a voxel size of 1x1x3 mm³.

The total scan duration will be approximately 30 minutes for both silicone or saline implants.

Follow-up MRIs: Subsequent MRIs will be performed in the prone position with a dedicated 16-channel breast coil. Parameters similar to baseline MRIs will be used for sequences. If a patient is unable to receive the baseline and/or follow-up MRI, or if either MRI produces images of insufficient quality for evaluation, the patient may still participate in and be evaluated for the rest of the study.

5.0 THERAPEUTIC/DIAGNOSTIC AGENTS

Multi-beam IMRT has been proven to be a feasible and safe method of PMRT delivery for locally advanced breast cancer patients. Following mastectomy and immediate implant-based reconstruction, multi-beam IMRT will be utilized to treat the chest wall, expander or permanent implant, and axillary, supraclavicular and internal mammary lymph nodes. The radiation dose (50-50.4 Gy/25-28 fractions in approximately 5-6 weeks), treatment-planning and delivery aspects are according to departmental guidelines for breast IMRT.

Concurrent biologic therapy (Trastuzumab, Tamoxifen or Aromatase Inhibitors) with radiation therapy will be permitted, but concurrent cytotoxic chemotherapy will not.

6.0 CRITERIA FOR SUBJECT ELIGIBILITY

6.1 Subject Inclusion Criteria

1. Females who are ≥ 18 years of age with a life expectancy estimated to be at least 2 years

2. Histologically-confirmed invasive breast cancer by MSKCC
3. Eastern Cooperative Oncology Group (ECOG) performance status of 0 or 1
4. Status post mastectomy with surgical assessment of axillary nodes
5. Immediate reconstruction with tissue expander (Group 2) or permanent implant (Group 1) prior to RT performed at MSKCC
6. If PMRT is recommended, the treatment fields will include the axillary, supraclavicular, and internal mammary nodes

6.2 Subject Exclusion Criteria

1. Absence of a breast reconstruction prior to RT (placement of tissue expander is sufficient for group 2)
2. Pregnant or breastfeeding
3. Psychiatric or addictive disorders that would preclude obtaining informed consent or filling out Breast-Q[®] questionnaires
4. Prior radiation therapy to the ipsilateral breast/nodes or thorax

The criterias outlined above apply to the patients enrolled to meet the primary objective of the study. Additional criteria for patients in the cardiac substudy portion of the protocol are outlined in Section 7.1.2.

7.0 RECRUITMENT PLAN (Limited Waiver of Authorization)

Patients will be identified at consultation in the Radiation Oncology clinics for their eligibility. The investigators take due notice of the National Institutes of Health (NIH) policy concerning inclusion of women and minorities in clinical research populations.

Potential research subjects will be identified by a member of the patient's treatment team, the protocol investigator, or research team at Memorial Sloan-Kettering Cancer Center (MSKCC). If the investigator is a member of the treatment team, they will screen their patient's medical records for suitable research study participants and discuss the study and their potential for enrolling in the research study. Potential subjects contacted by their treating physician will be referred to the investigator/research staff of the study.

The principal investigator may also screen the medical records of patients with whom they do not have a treatment relationship for the limited purpose of identifying patients who would be eligible to enroll in the study and to record appropriate contact information in order to approach these patients regarding the possibility of enrolling in the study.

During the initial conversation between the investigator/research staff and the patient, the patient may be asked to provide certain health information that is necessary to the recruitment and enrollment process. The investigator/research staff may also review portions of their medical records at MSKCC in order to further assess eligibility. They will use the information provided by the patient and/or medical record to confirm that the patient is eligible and to contact the patient regarding study enrollment. If the

patient turns out to be ineligible for the research study, the research staff will destroy all information collected on the patient during the initial conversation and medical records review, except for any information that must be maintained for screening log purposes.

In most cases, the initial contact with the prospective subject will be conducted either by the treatment team, investigator or the research staff working in consultation with the treatment team. The recruitment process outlined presents no more than minimal risk to the privacy of the patients who are screened and minimal PHI will be maintained as part of a screening log. For these reasons, the study will seek a (partial) limited waiver of authorization for the purposes of (1) reviewing medical records to identify potential research subjects and obtain information relevant to the enrollment process; (2) conversing with patients regarding possible enrollment; (3) handling of PHI contained within those records and provided by the potential subjects; and (4) maintaining information in a screening log of patients approached (if applicable).

It is estimated that between 200-300 eligible patients are treated in the Department of Radiation Oncology per year, including the Main campus and satellite facilities. On average, 20-25 eligible patients are under treatment at any moment, providing a large pool of patients who could be eligible for this study. Based on these estimates as well as the accrual history with IRB protocol #10-025, it is predicted that the study will meet the target accrual goal of 130 patients within three to four years.

7.1 Voluntary Studies: Assessment of Cardiotoxicities and Quality of Life

Patients enrolled in this protocol are eligible to volunteer to be evaluated in one of the sub-studies below. Participation in these adjunct interventions is strictly voluntary and not required to assess the primary endpoint of the protocol, which is assessment of implant failure rates.

Given the large population of breast cancer patients who receive neoadjuvant chemotherapy for breast cancer and our departmental policy of pre-operatively evaluating such patients for radiation, the study plans to identify and recruit the patients needed for n=10 patients required for the —control group (Group 2B). Potential candidates will be identified at the time of pre-operative consultation in the radiation oncology department. It is customary for patients who have received neoadjuvant chemotherapy to be seen in a subsequent new visit following surgery, in order to discuss how response to chemotherapy impacts radiation treatment recommendations. At that time, if radiation therapy is not recommended, the patient will be offered enrollment onto the control arm (no RT) of the sub-study assessing early cardiotoxicity.

7.1.1 Ammonia PET Scans to Correlate IMRT Dose to the Heart

Patients who meet the exclusion criteria listed below (in addition to those listed in section 6.0) will be approached regarding volunteering to receive a $^{13}\text{N-NH}_3$ PET/CT scan during RT simulation, as well as 12-18 months (\pm 6 months) after completion of RT. Ten volunteer patients are expected (n=10, all left-sided), but the study has budgeted enough scans for twelve patients, in the event that a patient is lost to follow-up/expires and cannot have the second scan, or declines the second scan.

Any of the following excludes a patient from the PET/CT subset:

- a. Age >60 years old at time of diagnosis

- b. Diabetes mellitus
- c. Hyperlipidemia
- d. Obesity
- e. Personal history of cardiac illness
- f. Planned IMRT to the right reconstructed breast

7.1.2 Detection of Early Subclinical Cardiotoxicities (Following IMRT)

A total of 20 patients will be required for this voluntary portion of the study:

7.1.2.1 Group 2A

Group 2A (n=10) are patients who will be receiving intensity-modulated radiation therapy to the (reconstructed) breast and regional lymph nodes. They will be approached regarding volunteering to receive the evaluations for assessment of cardiotoxicity and functional performance status outlined in Section 10.0. These evaluations will be performed 0-4 weeks prior to radiation therapy and 2-4 weeks after completion of radiation therapy.

7.1.2.2 Group 2B

Group 2B (n=10) are patients who are receiving neoadjuvant chemotherapy and mastectomy, evaluated by Radiation Oncology for consideration of RT but do not receive RT. These 10 patients will serve as a control population against which to compare the effect of IMRT on early subclinical cardiotoxicity, and will be approached to receive the identical evaluations for assessment of cardiotoxicity as the 10 patients in the experimental group who do receive IMRT. The assessments for the control group will be performed at similar post-operative intervals as the experimental group: 4-8 weeks after surgery and at 15-20 weeks after surgery.

For breast cancer patients who receive neoadjuvant chemotherapy, it is customary for the Department of Radiation Oncology to preliminarily evaluate at a time point prior to the receipt of mastectomy. This allows adequate time for planning and sequencing of treatments, in the event that the patient opts for immediate reconstruction. After the mastectomy, the patient is seen for a second, subsequent new visit, at which time final pathology from the mastectomy is available to guide definitive treatment recommendations. We will plan to identify potential candidates for both the control and experimental arms at the first new visit prior to surgery and follow up with/enroll eligible volunteers at the second visit.

Patients in Groups 2A and 2B must meet the following inclusion criteria:

- a. Normal cardiac function (left ventricular ejection fraction $\geq 50\%$)
- b. Able to complete an acceptable baseline CPET, as determined by the absence of remarkable ECG findings or other inappropriate response to exercise
- c. Able to achieve an acceptable peak baseline CPET, as defined by any of the following criteria:

- i. achieving a plateau in oxygen consumption, concurrent with an increase in power output;
- ii. a respiratory exchange ratio ≥ 1.10 ;
- iii. attainment of maximal predicted heart rate (HR_{max}) (i.e within 10 bpm of age-predicted HR_{max} [$HR_{max}=220-Age(years)$]);
- iv. volitional exhaustion, as measured by a rating of perceived exertion (RPE) ≥ 18 on the BORG scale.

- d. Medical clearance from attending oncologist or attending radiation oncologist to undergo a symptom-limited cardiopulmonary exercise test.

Any of the following will exclude a patient from participating in Group 2A or 2B:

- a. Any of the following contraindications to cardiopulmonary exercise testing
 - Acute myocardial infarction within 3–5 days of any planned study procedures;
 - Unstable angina;
 - Uncontrolled arrhythmia causing symptoms or hemodynamic compromise;
 - Recurrent syncope;
 - Active endocarditis;
 - Acute myocarditis or pericarditis;
 - Symptomatic severe aortic stenosis;
 - Uncontrolled heart failure;
 - Acute pulmonary embolus or pulmonary infarction within 3 months of any planned study procedures;
 - Thrombosis of lower extremities;
 - Suspected dissecting aneurysm;
 - Uncontrolled asthma;
 - Pulmonary edema;
 - Room air desaturation at rest $\leq 85\%$;
 - Respiratory failure;
 - Acute non-cardiopulmonary disorders that may affect exercise performance or be aggravated by exercise (i.e., infection, renal failure, thyrotoxicosis); or
 - Mental impairment leading to inability to cooperate.
- b. Lymphedema of the upper extremities, as detected on history and physical
- c. Any condition that, in the opinion of the investigator, would preclude safe and adequate test performance

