9.2 Treatment and Set-up

Treatment will be delivered over approximately 5-6 weeks in 25-28 fractions, utilizing 6 MV photons. A daily bolus will be applied over the chest wall. The number of gantry angles used for the multi-beam IMRT plan will be optimized for each patient but will generally range between 6-12 beams. The

radiation oncologist will delineate the PTV (planning target volume), according to guidelines specified in Appendix 3.

Two techniques are currently available in the Department of Radiation Oncology and will be employed to verify setup accuracy prior to each treatment:

1) AlignRT employs three ceiling-mounted stereostopic camera units to produce high-resolution and accurate 3D surface image referenced to the treatment isocenter. At each treatment fraction, the system images the current patient position instantaneously. State-of-the-art surface-matching software registers these data to the reference surface within seconds. Couch shifts are displayed to show discrepancies between existing and ideal treatment positions. New coordinates for the optimal couch position are then displayed and may be applied. This system has been FDA-approved. Further information regarding this approval is available on the website:

http://www.visionrt.com/site_files/AlignRT%20SE%20FDA%20Clearance%20Letter.pdf

A 2-step setup procedure has been established to minimize breast tissue deformation. First, the patient's arm and chin will be aligned to match simulation position with real-time AlignRT guidance, to minimize difference in muscle stretching. Then the patient's chest wall surface (including the ipsilateral reconstructed breast and 1/3 of contralateral breast) will be used as the region of interest for alignment.

2) An orthogonal pair of KV images allows optimal visualization of bony anatomy as well as clips in the axilla or the port in a tissue expander. One Trilogy, two 2100EX linear accelerators, and two True Beam linear accelerators with on-board KV imagers are available in the department. Bony landmarks, such as anterior ribs, should be used for alignment at the setup.

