9.2.1 Treatment interruptions

In the event that a patient must miss a scheduled treatment for non-toxicity related reasons (ie: weather, sickness, family emergencies, etc) the treatment visit will be made up at the end. If the patient misses more than 5 consecutive treatments, they will be removed from the protocol and considered inevaluable.

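### Control visits in the cardiotoxicity sub-study match the IMRT patients' post-operative timing only if IMRT starts about 8-10 weeks after mastectomy, which the protocol does not state

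*Combined protocol and SAP*

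**What the plan says.** Section 7.1.2.2 ties the no-RT controls (Group 2B, n=10) to surgery: "The assessments for the control group will be performed at similar post-operative intervals as the experimental group: 4-8 weeks after surgery", with a second visit at 15-20 weeks. Section 10.2.2, the Group 2B schedule table and section 16.1 repeat these windows.

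The IMRT patients (Group 2A, n=10) are tied to radiation. Section 7.1.2.1: "These evaluations will be performed 0-4 weeks prior to radiation therapy and 2-4 weeks after completion of radiation therapy". No section expresses a 2A visit in weeks from surgery.

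The only link between the two clocks is the IMRT start. Section 4.2.2: "Multi-beam IMRT will be performed at least 4 weeks after mastectomy in Group 2, although it may be performed sooner". The earlier start is left to the physician's judgement of surgical recovery. Section 4.2.1 says the same for neoadjuvant patients. Neither gives an upper limit. Section 9.2 gives the duration: "Treatment will be delivered over approximately 5-6 weeks in 25-28 fractions".

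Section 14.1.4 compares the groups with Wilcoxon rank sum and Fisher exact tests. It does not mention time since surgery, and it does not say whether follow-up values or changes from baseline are compared.

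**The concern.** The controls exist so that the 2A results can be read against patients who had neoadjuvant chemotherapy and mastectomy but no radiation. Assignment is not randomised, so visits at the same stage after surgery are one of the few safeguards the design has. Exercise capacity, fatigue, quality of life and inflammatory markers may plausibly still be changing in the months after mastectomy and chemotherapy. If one group is tested systematically earlier after surgery, a difference in recovery would appear in the comparison as an IMRT effect, or could mask one.

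The protocol asserts that the timing is similar, but the windows it gives do not guarantee it, and nothing in the analysis section would correct a mismatch.

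**Working it through.** **Inputs**
- IMRT start after mastectomy, S weeks: at least 4, sooner allowed, no maximum (4.2.1, 4.2.2).
- IMRT duration: 5-6 weeks (9.2).
- 2A baseline: 0-4 weeks before IMRT. 2A follow-up: 2-4 weeks after IMRT ends (7.1.2.1).
- 2B windows: weeks 4-8 and 15-20 after surgery (7.1.2.2).

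**Formulas, in weeks after mastectomy**
- 2A baseline: S−4 to S, not before week 0.
- 2A follow-up: S+5+2 to S+6+4, that is S+7 to S+10, with midpoint S+8.5.
- 2B follow-up midpoint: (15+20)/2 = 17.5.

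**Can the plan's own windows be reproduced?** Yes, for particular starts. S = 8 gives a baseline of 4-8, identical to the controls, and a follow-up of 15-18. Letting S run from 8 to 10 gives follow-ups from 15 to 20, the whole control window. Such a start is nowhere stated.

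**Other starts**

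| S | 2A baseline | Shared with 4-8 | 2A follow-up | Shared with 15-20 | 17.5 − (S+8.5) |
|---|---|---|---|---|---|
| 3 | 0-3 | none | 10-13 | none | 6 |
| 4 | 0-4 | week 4 only | 11-14 | none | 5 |
| 5 | 1-5 | 1 week | 12-15 | week 15 only | 4 |
| 6 | 2-6 | 2 weeks | 13-16 | 1 week | 3 |
| 8 | 4-8 | all | 15-18 | 3 weeks (inside) | 1 |
| 10 | 6-10 | 2 weeks | 17-20 | 3 weeks (inside) | −1 |
| 13 | 9-13 | none | 20-23 | week 20 only | −4 |
| 14 | 10-14 | none | 21-24 | none | −5 |

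The follow-up windows are disjoint when S+10 < 15 (S < 5) or S+7 > 20 (S > 13).

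**Share of 2A follow-ups inside the control window.** Assume, for illustration only, that duration is uniform on 5-6 weeks and the visit delay uniform on 2-4 weeks. The share is then 0% at S = 4 or 5, 25% at S = 6, 75% at S = 7, and 100% at S = 8 or 10.

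**Missed fractions.** Section 9.2.1 makes up missed treatments at the end. It also says: "If the patient misses more than 5 consecutive treatments, they will be removed from the protocol". One tolerated gap therefore adds about a week. At S = 4 the follow-up becomes 11-15, touching the control window at week 15 only.

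**Spacing between the two visits.** 2A: 0+5+2 = 7 to 4+6+4 = 14 weeks. 2B: 15−8 = 7 to 20−4 = 16 weeks. The spacing is similar, so the possible mismatch lies in where the visits fall after surgery, not in how far apart they are.

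**The case against.** The strongest reply is that 4 weeks is a floor, and that an earlier start is conditional on recovery from surgery. The control windows look as if they were derived from a start near week 8, where they fit very well, and the plan claims similarity, not identity. This stands. A reader might infer from the week-4 row that the two groups will not overlap; the documents do not support that, since starts of about 5 to 13 weeks give some contact at follow-up. What remains is that the required start is unstated and the permitted range extends well beyond it.

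Second, the week 0-4 baselines in the table are mostly theoretical. Volunteers are enrolled at the visit after mastectomy, once final pathology is available, and must then meet the ejection fraction, medical clearance and exercise test criteria. This also stands: the real baseline gap is probably smaller than the windows allow. It does not change the follow-up arithmetic.

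Third, similar visit spacing means that a comparison of change would reduce the imbalance. That is right, but it would not remove the imbalance if recovery is faster soon after surgery, and section 14.1.4 does not commit to change.

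Fourth, a reader might infer that Group 1 patients could enter Group 2A and be tested months later after mastectomy, because section 7.1.2.1 sets no limit and the 10.2.1 heading refers to the reconstructed breast. Other sections largely answer this. Section 9.4.1 says the 20 patients receive neoadjuvant chemotherapy; the schedule covering Group 2 and 2A is titled for tissue expander patients, and its footnote g places 2A within Group 2; and the Group 1 schedule has none of these tests. Only the wording needs tidying.

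Finally, this is an exploratory comparison that the plan itself calls preliminary, without a decision rule. Its controls are patients for whom RT was not recommended, a difference that no visit schedule can remove. Both points limit the weight of the concern, but a cheap repair is still worthwhile.

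**Conclusion.** The stated similarity of post-operative timing is not secured by the protocol's own windows. It holds well for IMRT starts of about 8-10 weeks after mastectomy, partly at week 6, and not at all at follow-up for starts before week 5 or after week 13. At the stated 4-week minimum, the follow-up midpoints are 5 weeks apart (12.5 v 17.5), with the IMRT patients tested earlier.

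The unadjusted 10 v 10 tests would carry any resulting difference in recovery into the IMRT comparison. How large that is, and in which direction, cannot be computed. A reader might multiply the 5-week gap by an assumed recovery of 1-2% per week to obtain a spurious 5-10% difference in peak oxygen consumption. The documents give no such rate and do not show that recovery continues that late, so the figure should not be used. Nor do they establish that IMRT would be made to look harmful; that depends on patients still improving and on whether levels or changes are compared.

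The conclusion assumes the stated 5-6 week treatment duration and that visits occur within their windows. It concerns the exploratory sub-study only. The implant-failure endpoint is unaffected.

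**What to change.** Leave IMRT timing and patient care as they are, and adjust the control schedule and the analysis.

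1. In 7.1.2.2, 10.2.2, 16.1 and the Group 2B table, set the control windows from the weeks since mastectomy observed at the Group 2A visits. Group-level windows suffice; one-to-one pairing is not needed.
2. Record weeks from mastectomy and from last chemotherapy at every 2A and 2B visit, and report both beside each comparison. Section 8.0 already collects surgery and chemotherapy details, so little new data capture is needed.
3. State in 14.1.4 that change from baseline is compared between groups.
4. As a wording clarification only, reconcile 7.1.2.1 and the 10.2.1 heading with 9.4.1 and the Group 2/2A schedule, which describe neoadjuvant, tissue expander patients.

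The visits, tests and patient numbers stay the same. The one practical cost is that some control visits must be booked in step with 2A accrual.
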